2.7.2 Deaths

See [Section 2.7.1](#). A listing will be provided of all deaths, deaths outside of on-treatment period will be flagged. This all deaths listing will be for “All screened patients” so that deaths during screening are also presented.

2.7.3 Laboratory data

Laboratory values (central and local) are converted to the international system of units (SI). CTCAE Grade 0 will be assigned for all non-missing values not graded as 1 or higher. Grade 5 will not be used. For laboratory tests where grades are not defined by CTCAE version 4.03, results will be categorized as low/normal/high based on laboratory normal ranges.

The following summaries will be generated separately for hematology and for the safety set:

- Shift tables by CTCAE grade (or low/normal/high classification) to compare baseline to the worst on-treatment value:
 - Hematology: Neutrophils (absolute), platelets and hemoglobin
 - Chemistry: Creatinine, total bilirubin (TBL), aspartate aminotransferase (AST), alanine aminotransferase (ALT) and alkaline phosphatase (ALP)
- Summary statistics on platelets for change from baseline for months 3, 6, 12 and 24 will be provided. On-treatment platelet values will be used up to Month 24.
- Box plots showing parameter values over time (baseline and on-treatment time points 3, 6, 12 and 24 months) will be displayed based on time windows for the following selected parameters: Neutrophils (absolute), platelets, reticulocytes, hemoglobin and RBCs. Boxplots will display boxes (25th – 75th percentiles) and median (line) as well as joint mean (dot) values. Whiskers extend to the 10th – 90th percentiles with any values outside the whiskers not being displayed. A footnote will explain that these values are not displayed. However, all values are used to calculate mean and percentiles displayed on the graph. The number of observations used for this analysis is to be stated at the bottom.

Listings of laboratory data (hematology and biochemistry) will be provided showing the corresponding CTCAE grades, if applicable, and the classifications relative to the laboratory normal ranges. Values measured outside of on-treatment period will be flagged.

Liver function parameters

Liver function parameters of interest are TBL, ALT, AST and ALP.

The number (%) of patients with worst on-treatment values will be summarised:

- ALT or AST > 3xULN
- ALT or AST > 5xULN
- ALT or AST > 8xULN
- ALT or AST > 10xULN
- ALT or AST > 20xULN
- TBL > 2xULN
- TBL > 3xULN
- ALT or AST > 3xULN & TBL > 2xULN
- ALT or AST > 3xULN & TBL > 2xULN & ALP \geq 2xULN
- ALT or AST > 3xULN & TBL > 2xULN & ALP < 2xULN (potential Hy's law)

Listings of liver event data will be provided. Values measured outside of on-treatment period will be flagged.

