
All dose modifications should be based on the worst preceding toxicity.
 
^a Common Toxicity Criteria for Adverse Events (CTCAE Version 4.03)
 
^b Core LFTs consist of ALT, AST, GGT, total bilirubin (fractionated [direct and indirect], if total bilirubin $>$ 2.0 \times ULN), and alkaline phosphatase (fractionated [quantification of isoforms], if alkaline phosphatase $>$ 2.0 \times ULN.)
 
^c "Combined" defined as total bilirubin increase to the defined threshold concurrently with ALT/AST increase to the defined threshold
 
If combined elevations of AST or ALT and total bilirubin do not meet the defined thresholds, please follow the instructions for isolated elevation of total bilirubin and isolated elevation of AST/ALT, and take a conservative action based on the degree of the elevations (e.g. discontinue treatment at the situation when omit dose is needed for one parameter and discontinue treatment is required for another parameter). After all elevations resolve to the defined thresholds that allow treatment re-initiation, re-start the treatment either at the same dose or at one dose lower if criterion for dose reduction is met.
 
^d "Cholestasis" defined as ALP elevation ($>$2.0 xULN and R value $<$2) in patients without bone metastasis, or elevation of ALP liver fraction in patients with bone metastasis. The R value is calculated by dividing the ALT by the ALP, using multiples of the ULN for both values. It denotes whether the relative pattern of ALT and/or ALP elevation is due to cholestatic (R \leq 2), hepatocellular (R \geq 5), or mixed (R $>$2 and $<$ 5) liver injury.
 
^e "One dose level" defined as eltrombopag dose reduction by 25 mg.
	

Eltrombopag can cause hepatobiliary laboratory abnormalities, severe hepatotoxicity, and potentially fatal liver injury. Serum ALT, AST and bilirubin should be measured prior to initiation of eltrombopag, every 2 weeks during the dose adjustment phase and monthly after establishment of a stable dose. Abnormal serum liver tests should be evaluated with repeat testing as described in [Table 6-7](#). If the abnormalities are confirmed, serum liver tests should be monitored weekly until the abnormalities resolve, stabilize, or return to baseline levels.

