6.3.4.1 Follow-up on potential drug-induced liver injury (DILI) cases

Patients with transaminase increase combined with TBIL increase may be indicative of potential DILI, and should be considered as clinically important events.

The threshold for potential DILI may depend on the patient's baseline AST/ALT and TBIL value; patients meeting any of the following criteria must require further follow-up as outlined below:

- For patients with normal ALT and AST and TBIL value at baseline: [AST or ALT > 3.0 x ULN] combined with [TBIL > 2.0 x ULN] OR [INR > 1.5] without evidence of cholestasis (no ALP elevation)
- For patients with elevated AST or ALT or TBIL value at baseline: [AST or ALT > 2 x baseline AND > 3.0 x ULN] OR [AST or ALT > 8.0 x ULN], combined with [TBIL > 2 x baseline AND > 2.0 x ULN]
- For subjects with normal baseline ALT: [ALT \geq 5.0 x ULN]

Medical review must ensure that liver test elevations are not caused by cholestasis, defined as ALP elevation > 2.0 x ULN with R value < 2 in patients without bone metastasis, or elevation of ALP liver fraction in patients with bone metastasis.

Note: (The R value is calculated by dividing the ALT by the ALP, using multiples of the ULN for both values. It denotes whether the relative pattern of ALT and/or ALP elevation is due to cholestatic (R \leq 2), hepatocellular (R \geq 5), or mixed (R > 2 and < 5) liver injury).

In the absence of cholestasis, these patients must be immediately discontinued from study drug treatment, and repeat LFT testing as soon as possible, preferably within 48 hours from the awareness of the abnormal results. The evaluation must include laboratory tests, detailed history, physical assessment and the possibility of liver metastasis or new liver lesions, obstructions/compressions, etc.

1. Laboratory tests must include ALT, AST, albumin, creatine kinase, total bilirubin, direct and indirect bilirubin, GGT, prothrombin time (PT)/INR and alkaline phosphatase.
2. A detailed history, including relevant information, such as review of ethanol, concomitant medications, herbal remedies, supplement consumption, history of any pre-existing liver conditions or risk factors, must be collected.
3. Further testing for acute hepatitis A, B, C or E infection and liver imaging (e.g., biliary tract) may be warranted.
4. Obtain PK sample, as close as possible to last dose of study drug, if PK analysis is performed in the study.

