The reference start date for all assessments (safety, efficacy, patient reported outcomes (PROs), etc.) will be the start date of study treatment.

The study day will be displayed in the data listings. If an event starts before the reference start date, the study day displayed in the listing will be negative.

Baseline

Baseline is the result of an investigation describing the “true” uninfluenced state of the patient, defined as the period from the date of signing any informed consent document to the start date of study treatment. Assessments, specified to be collected post-dose on the first date of study treatment are not considered.

The last non-missing assessment, including unscheduled assessments on or before the date of start of study treatment is defined as “baseline value” or “baseline assessment”.

Where multiple measurements meet the baseline definition, with no further flag or label that can identify the chronological order, then values from central assessments should be considered as baseline rather than local values.

For electrocardiogram (ECG) parameters, if there are multiple replicates per time point, the average of these measurements would be calculated for baseline (if not already available in the database).

If patients have no value as defined above, the baseline result will be missing.

Observation periods

The overall observation period will be divided into three mutually exclusive segments:

1. **Pre-treatment:** from day of patient’s informed consent to start date of study treatment
2. **On-treatment:** from start date study treatment to last date of study treatment + 30 days
3. **Post-treatment:** from last date of study treatment + 31 days

On-treatment assessments/events

The definition of on-treatment is given below, depending on the context.

For safety summary tables an on-treatment AE is defined as any AE reported in the following time interval (including the lower and upper limits):

- <date of first administration of study treatment; date of last administration of study treatment + 30 days>

This corresponds to the definition of treatment-emergent AEs given in the protocol, i.e. AEs which are newly reported or worsening from baseline.

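### The combined liver rows in SAP 2.7.3, including potential Hy's law, use worst values with no concurrency rule and can misclassify patients

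*SAP*

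**What the plan says.** SAP 2.7.3 (Liver function parameters) introduces the list of liver rows with "The number (%) of patients with worst on-treatment values will be summarised". The list holds single-parameter rows (ALT or AST above 3, 5, 8, 10 and 20xULN; TBL above 2 and 3xULN) and three combined rows. One combined row is ALT/AST >3xULN with TBL >2xULN. The other two split it by ALP at 2xULN. The row "ALT or AST > 3xULN & TBL > 2xULN & ALP < 2xULN" carries the label potential Hy's law. No same-sample or time-window rule is given for any of them.

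SAP 2.1.3 defines the on-treatment period as "from start date study treatment to last date of study treatment + 30 days". That is about 7 months for a non-responder who completes treatment (6 months plus 30 days) and about 25 months for a responder who completes cyclosporine (24 months plus 30 days).

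The protocol is specific about timing. Table 6-7, footnote c, defines combined as "total bilirubin increase to the defined threshold concurrently with ALT/AST increase to the defined threshold". On cholestasis it has two wordings. Footnote d and the medical-review paragraph of 6.3.4.1 use ALP together with an R value; the latter reads "defined as ALP elevation > 2.0 x ULN with R value < 2 in patients without bone metastasis". The first criterion in 6.3.4.1 instead explains absence of cholestasis simply as ALP not being elevated.

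**The concern.** A worst value is a clear summary for one parameter. A row joined by an ampersand needs a statement of when the values must hold together, and a per-patient maximum removes that information. Two errors follow.

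- **Over-counting.** Peak ALT/AST in one month and peak TBL in another satisfy the combined row although no sample showed both. The protocol makes separate bilirubin rises plausible. Section 1.2.1.2.3 describes inhibition of bilirubin glucuronidation and transport by eltrombopag. It also reports that in the refractory-SAA study six patients had TBL >1.5xULN, all from indirect bilirubin, while only two had ALT or AST >3xULN with concurrent bilirubin elevation.
- **Mislabelling.** The maximum ALP may come from a different date than the ALT/AST and TBL elevation. A concurrent case with low ALP at the time is then moved to the ALP >= 2xULN row by an unrelated later value.

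At stake is whether the count beside the potential Hy's law label can be read as it will naturally be read, and whether it agrees with the cases handled under protocol 6.3.4.1.

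**Working it through.** The plan gives no expected count for this table, so there is no figure to reproduce. The check applies the SAP rule and a same-sample rule to constructed patients.

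**Rules** (all values in multiples of ULN)

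- SAP as written: take max ALT/AST, max TBL and max ALP over all samples. Combined if max ALT/AST >3 and max TBL >2; potential Hy's law if also max ALP <2.
- Same sample, SAP's ALP cut: ALT/AST >3, TBL >2 and ALP <2 in one sample.
- Same sample, protocol ALP-plus-R wording: ALT/AST >3 and TBL >2 in one sample, and not (ALP >2 and R <2). Protocol 6.3.4.1 defines R: "The R value is calculated by dividing the ALT by the ALP, using multiples of the ULN for both values".

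| Case | Samples (ALT, TBL, ALP) | SAP as written | Same sample, ALP <2 | Same sample, ALP plus R |
|---|---|---|---|---|
| A | (4, 1, 1), later (1, 2.5, 1) | Hy's law row | not combined | not combined |
| B | (6, 3, 1.2), later (1, 1, 2.4) | ALP >= 2 row | Hy's law row | Hy's law row, R = 6/1.2 = 5.0 |
| C | (15, 3, 2.5) | ALP >= 2 row | ALP >= 2 row | Hy's law row, R = 15/2.5 = 6.0 |
| C2 | (6, 3, 2.5) | ALP >= 2 row | ALP >= 2 row | Hy's law row, R = 6/2.5 = 2.4 |
| D | (4, 3, 3) | ALP >= 2 row | ALP >= 2 row | cholestatic, R = 4/3 = 1.33 |
| E | (6, 3, 1.2) | Hy's law row | Hy's law row | Hy's law row, R = 5.0 |

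Cases A and B are errors of timing. They change under either same-sample rule, whichever ALP rule is used. If the first ALP in case B is put at 0.9, there is no ALP elevation on any reading (R = 6/0.9 = 6.67), and the SAP still moves the patient because of the later 2.4. Cases C and C2 differ only if the ALP-plus-R wording is the intended one. D and E are classified alike throughout.

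**How easily peaks miss each other.** Suppose a patient has k visits with high ALT/AST and m with high TBL, placed at random among V visits. The chance that they never coincide is C(V-k, m)/C(V, m). Counting from Tables 7-1 and 7-2, V is 16 post-baseline visits to week 26 and 38 to month 24.

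| k = m | V = 16 | V = 38 |
|---|---|---|
| 1 | 15/16 = 0.94 | 37/38 = 0.97 |
| 2 | 91/120 = 0.76 | 630/703 = 0.90 |
| 3 | 286/560 = 0.51 | 6545/8436 = 0.78 |
| 4 | 495/1820 = 0.27 | 46376/73815 = 0.63 |

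Random placement is an assumption. ALT and TBL rises probably tend to occur together, so these are upper-end illustrations. They apply only to a patient who has both kinds of high visit, and say nothing about how many such patients there will be.

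**What cannot go wrong.** If one sample has ALT/AST >3 and TBL >2, both maxima pass as well. The unsplit row can therefore over-count but not under-count on those thresholds.

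**The case against.** The best defence has four parts.

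1. **Nothing is lost.** A patient moved out of the labelled row remains in the unsplit row and the ALP >= 2xULN row. Protocol 6.3.4.1 requires cases confirmed on repeat testing, with no alternative cause, to be reported as SAEs. AESI tables and liver listings are also planned; SAP section 4 restricts the listings to key parameters but keeps the hepatic ones. This stands. A reader might infer that the table hides drug-induced liver injury from the study, and the documents do not support that.
2. **The detail may sit elsewhere.** SAP section 1 places variable derivations and table shells in separate documents, which may contain a timing rule. That is possible, but the SAP text itself states worst values and no more.
3. **The protocol is a limited benchmark.** Footnote c belongs to a dose-adjustment table, and protocol 10.5.3.3 plans no combined liver table, so no planned analysis is contradicted. A reader might also infer that an ALP-only split breaks the protocol's definition of cholestasis. Because 6.3.4.1 carries two wordings, that is not established. The timing problem in cases A and B does not depend on it.
4. **A same-sample rule has its own blind spot.** Under protocol 7.1, visits are two weeks apart after month 2 and four weeks apart after month 9. ALT may cross its threshold at one visit and TBL at the next. This is a fair point, and the fix must allow for it.

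**Conclusion.** The point holds as one of misclassification within the summary table. Followed as written, SAP 2.7.3 can place a patient without any concurrent elevation in the potential Hy's law row, and can take a patient with one out of it. This rests on the SAP text alone and assumes that no unseen specification overrides it.

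No expected count can be derived. A reader might multiply the adverse-event rates in protocol 1.2.1.2.3 (29.3% for a transaminase increase, 17.4% for a bilirubin increase) by 54, giving 0.293 x 0.174 x 54 = 2.75, and take that as false cases. It is not. Those are event-reporting rates from a regimen that included h-ATG, not frequencies above 3xULN and 2xULN. The product assumes independence, and it would include truly concurrent cases. What can be said is that one patient is 1/54 = 1.9% of those enrolled. The same protocol section reports that no case in the first-line study met DILI or Hy's law criteria, so a single misplaced patient could be the difference between a zero and a non-zero row. That this would change the overall liver safety conclusion is not shown, since shift, AESI and SAE tables also bear on it.

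**What to change.** In SAP 2.7.3:

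- Keep worst on-treatment values for the single-parameter rows.
- Derive the three combined rows from ALT/AST, TBL and ALP in the same sample.
- Keep the existing any-time version of ALT/AST >3xULN with TBL >2xULN as a separate row labelled as screening. Peaks at adjacent visits are then not lost, and the final report stays comparable with the primary CSR already written.
- Reconcile the two cholestasis wordings in protocol 6.3.4.1 and state which one the analysis row uses. Show the R value for any flagged patient with ALP >= 2xULN.
- List every flagged patient with sample dates, direct and indirect bilirubin, ALP and R.

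The cost is one extra row and a small amount of programming. Protocol Tables 7-3 and 7-5 put the tests in one chemistry category, so no new data are needed. No dosing or stopping rule is affected, and the SAP describes the final analysis as still to be done.

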2.7.4 Other safety data

2.7.4.1 ECG

12-lead ECGs, including QTcF (Fridericia's correction), mean heart rate (HR), PR-, QT- and QRS-durations, will be obtained locally for each patient during the study. ECG data will be read and interpreted locally.

Where ECG replicates are provided for an assessment, the average of the ECG parameters at that assessment will be used in the analyses.

The number (%) of patients with notable values will be presented.

Table 2-3 Notable criteria for ECG parameters

Parameter	Notable low value	Notable high value
QTcF		New value of >450 and \leq 480 ms New value of >480 and \leq 500 ms New value of >500 ms Increase from baseline of >30 ms to \leq 60 ms Increase from baseline of >60 ms
Heart rate	Decrease >25% from baseline and to a value <50 bpm	Increase >25% from baseline and to a value >100 bpm
PR	--	Increase >25% from baseline and to a value >200 ms New value of >200 ms
QRS	--	Increase >25% from baseline and to a value >120 ms New value of >120 ms

A listing of all ECG assessments will be produced. Notable values as well as values measured outside of on-treatment period will be flagged in the listings.

2.7.4.2 Vital signs

Vital sign assessments are performed in order to characterise basic body function. The following parameters were collected: height (cm, inch), weight (kg, pound), body temperature (°C, Fahrenheit), position, pulse (beats/minute), systolic and diastolic blood pressure (mmHg).

The number (%) of patients with notable values will be presented.

Table 2-4 Notable criteria for vital signs

Vital sign (unit)	Notable low value	Notable high value
Weight (kg)	decrease \geq 10% from baseline	increase \geq 10% from baseline
Body temperature (°C)	--	\geq 39.1
Pulse rate (bpm)	\leq 50 and decrease from baseline of $>25\%$	\geq 100 and increase from baseline of $>25\%$
Systolic blood pressure (mmHg)	\leq 90 and decrease from baseline of ≥ 20	\geq 180 and increase from baseline of ≥ 20
Diastolic blood pressure (mmHg)	\leq 50 and decrease from baseline of ≥ 15	\geq 105 and increase from baseline of ≥ 15

A listing of all vital sign assessments will be produced and notable values will be flagged. Assessments collected outside of on-treatment period will be flagged.

ECOG performance status

The eastern cooperative oncology group (ECOG) performance status will be used to assess physical health of patients, ranging from 0 (most active) to 5 (least active).

Shift tables comparing the baseline status with the worst post-baseline status will be provided.

Table 2-5 ECOG performance scale

Score	Description
0	Fully active, able to carry on all pre-disease performance without restriction
1	Restricted in physically strenuous activity but ambulatory and able to carry out work of a light or sedentary nature, e.g., light house work, office work
2	Ambulatory and capable of all self-care but unable to carry out any work activities. Up and about more than 50% of waking hours
3	Capable of only limited self-care, confined to bed or chair more than 50% of waking hours
4	Completely disabled. Cannot carry on any self-care. Totally confined to bed or chair
5	Dead

A listing of all ECOG performance status assessments will be produced, flagging assessments collected outside of the on-treatment period.

Ophthalmic and neurologic examinations

No summaries or listings as only collected as source data.

2.8 Pharmacokinetic endpoints

The PAS will be used for the PK data analysis and the FAS for the listings.

PK parameters for eltrombopag will be determined using non-compartmental methods using Phoenix (Pharsight, Mountain View, CA) or other appropriate software. PK parameters listed in the table below will be estimated and reported, when feasible.

Table 2-6 Non-compartmental PK parameters of eltrombopag

Parameter	Description
Cmax	Observed maximum plasma concentration following administration (mass/volume)
AUClast	Area under the curve calculated to the last quantifiable concentration point (Tlast) (mass*time/volume)
AUCtau	Area under the curve calculated to the end of the dosing interval (tau) (mass*time/volume)
Ctrough	Pre-dose plasma concentration (mass/volume)
Tmax	The time to reach peak or maximum concentration (time)
CLss/F	Apparent systemic (or total body) clearance at steady state from plasma (volume/time)

The concentrations obtained for the Week 2 pre-dose sample (sample 1) will be duplicated in order to also be analysed as a 24 h post-dose sample (and will be attributed sample number 6 for analysis purposes).

Descriptive statistics of all PK parameters and PK concentrations will include arithmetic and geometric mean, median, sd, and coefficient of variation (CV), geometric CV, minimum and maximum. Zero concentrations will not be included in the geometric mean calculation. Since Tmax is generally evaluated by a nonparametric method, only n, median values and ranges will be given for this parameter.

PK parameters and PK concentrations will be summarized descriptively by ethnicity subgroups (if at least 3 patients with PK parameters and/or concentrations in the subgroup) and overall. The PK parameters, Cmax, AUClast, AUCtau, and Ctrough, will be normalized to the protocol starting dose i.e. 100 mg for S/SE Asians and 150 mg for Others.

Individual PK concentrations will be listed. The PK sample/concentrations will be flagged in the listing when:

- 1- Patient changed or interrupted the dose during 7 days before PK sample collection
- 2- Patient changed the dose during the 2 weeks before PK sample collection
- 3- Patient vomited within 4 hours after dosing on day of PK assessment for post-dose samples, or on the day prior to sampling, for pre-dose samples
- 4- PK sample was collected out of time interval for the 24-hour sample, the time window considered is 20-28 hours

These flags will be programmatically set up during the PK merge with the clinical database. For the first three PK flags the sample will be excluded from the analysis for PK parameter calculation and from the descriptive statistics of concentrations over scheduled sample

collection time. For the fourth PK flag the sample will be excluded from the descriptive statistics of concentrations over scheduled sample collection time only.

In addition, during analysis the pharmacokinetics will flag PK samples/concentrations when dose, sample collection time and/or concentration value are missing, as well if pre-dose samples are collected post-dose. Those PK samples/concentrations will be excluded from the analysis for PK parameter calculation and from the descriptive statistics of concentrations over scheduled sample collection time.

All individual PK parameters and PK concentrations will be listed. Those PK concentrations or PK parameters not evaluable for statistical analysis will be flagged and the reason for exclusion will be given in the listings.

The following analyses and results may be performed and reported separately from the CSR:

Exposure-response analysis will be conducted, if supported by the data to evaluate relationship between exposure of eltrombopag and response and specific AEs of special interests. These relationships will be explored by graphical methods. Any apparent relationship may be further characterized by a model as appropriate and supported by the data.

Population PK may be performed if supported by the data to explore relevant covariates.

Handling of PK data below LLOQ or missing

Missing concentration values will be reported as such in data listings. Concentration values below the LLOQ will be handled as zero in summary statistics, and reported as such in data listings. Any missing PK parameter data will not be imputed.

